# 8.3.3.2. Multiplicity Adjustment

Not applicable.

### 8.3.3.4. Supportive Analysis of Primary Endpoint

The primary analysis will be repeated **the second s** 

### 8.3.3.5. Subgroup Analyses of Primary Analysis

Primary endpoint will be analyzed using a similar MMRM model in Section 8.3.3.1 for the following subgroups:

- Baseline MoCA:  $15-17, \ge 18$
- Baseline CDR: 0.5, 1
- Age:  $\leq 65, > 65$
- Race (Black or African American, White, Other)
- Sex (Male, Female)
- Baseline WAIS-IV (<Median, >=Median)
- Baseline RBANS (<Median, >=Median)
- Years of Education (<Median, >=Median)

Median categories are calculated from the overall baseline value and rounded to the nearest integer.

A summary using descriptive statistics on observed values, percent change from baseline and change from baseline by treatment group and subgroup will be provided. The primary endpoint by subgroup will be analyzed using MMRM only if there are at least 10 participants per subgroup. A forest plot showing the LSM and 95% CI bar at Day 84 within each subgroup and treatment group will be provided.

### 8.3.4. Analysis of Secondary Efficacy Variables

Not applicable.

8.3.5.

8.3.5.1.	I
8.3.5.2.	
8.3.5.3.	
8.3.5.4.	

8.3.5.5.		
8.3.5.6.		
8.3.5.7.		
8.3.5.8.		

		]
8.3.5.10.		
8.3.5.11.		
8.3.5.11.		
8.3.5.11.		
8.3.5.11.		
8.3.5.11.		
8.3.5.11.		

42

# 8.4. Safety Analysis

All safety summaries will be performed on the Safety Set using treatment received.

Safety and tolerability of SAGE-718 softgel lipid capsule

in participants with AD is the secondary objective of this study and will be evaluated by the frequency and severity of TEAEs, and withdrawal due to AEs. Other safety endpoints include change from baseline in vital signs, clinical laboratory analytes, ECGs,

The safety endpoints evaluated at scheduled visits are taken as done in nominal visit, without any windowing. If a value is available for a nominal scheduled visit, that value will be used in summary by visit. For the summary of the scheduled visits, unscheduled measurements and ET measurement, unless specified, will be included only if a scheduled measurement is not available, and the unscheduled measurement and ET measurement falls within the visit window for the scheduled visit (same as WAIS-IV Coding Test in Table 4). If there are two or more measurements in a visit window, the measurement taken closest to the study day target will be used in analysis. If the two have same distance from the target study day, the latter one will be used.

Anytime on treatment, last value on treatment and last value on study will be included in the summaries, unless specified. Anytime on treatment is defined as measurement on or after first dose, on or before the date of last dose. Last value on treatment is defined as the last post-baseline value between first dose of IP and up to the date of last dose of IP. Last value on study is defined as the last post-baseline value on or after the first dose of IP and on or before the last date of the study.

No statistical hypothesis testing will be conducted.

Safety data will be listed by participant and summarized by treatment group.

Safety Evaluation	Incidence	Source Data	Change from Baseline	Shift from Baseline	Potentially Clinically Significant	Abnormality/ Clinical Significance
AEs	X					
Clinical Laboratory		X	Х	Х	Х	*
ECG		Х	Х		Х	*
Vital Signs		Х	Х		Х	
Physical Exam		*				

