### 7.4. Dose Adjustment Criteria

Individual dose reductions will be permitted.

During the Treatment Period, participants will be able to receive IP as long as there are no dose limiting safety/tolerability concerns. Participants who cannot tolerate 1.2 mg will receive 0.9 mg for the remainder of the Treatment Period.

If dose adjustment is deemed necessary by the investigator at any time during the Treatment Period, the participant will return to the site to return any remaining IP and for the adjusted dose to be dispensed.

At the discretion of the investigator, participants who cannot tolerate the 0.9-mg dose may be discontinued from further IP administration refer to Section 8.4 for procedures for early IP discontinuation). Participants will be encouraged to continue to come in for the remaining study-related periodic assessments even after the IP discontinuation.

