#### 8.4.1. Investigational Product Discontinuation

Participants who discontinue IP will be invited by the investigator to complete all of the scheduled study visits and assessments. Those who may decline to continue participation will be asked to complete an Early Termination Visit.

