### 8.4.2. Clinical Laboratory

Any lab results considered clinically significant by the investigator will be captured as adverse events, hence will show up in AE displays.

Laboratory values contain ' $\geq$  x' or 'x  $\leq$ ' will be taken as the value of x in the analysis. If a laboratory value is reported as ' $\leq$ y' then y minus the minimum value with the same precision as y (ex. if y = 1.345, then use y - 0.001) will be used for the analysis. If a laboratory value is reported as '>y' then y plus the minimum value with the same precision as y will be used for the analysis. The same is true if the result is presented as below limit of quantification (BLQ) and a lower limit of quantification (LLOQ) value is provided – LLOQ value will be used for calculation in the summary tables. The actual results as collected will be displayed in the listings.

Results of continuous clinical laboratory parameters for hematology, biochemistry, coagulation, and urine samples for urinalysis at each scheduled visit and mean changes from baseline will be summarized in standard units. In addition, it will also include the summary of the last value on treatment and the last value on study.

Normal ranges for each parameter will be provided by the laboratory. Shift from baseline to post-baseline values in abnormality of hematology and biochemistry results will be summarized. In addition, shift from baseline to post-baseline values in abnormality of results at anytime on treatment where the worst value is used, the last value on treatment and the last value on study will be summarized. If a participant has both low and high post-baseline records, the participant will be counted twice for each low and high cell.

Clinical laboratory results will be listed by participant and timing of collection for each treatment group.

The number and percentage of participants with potentially clinical significance (PCS) values for each laboratory parameter will be summarized by treatment for anytime on treatment, the last value on treatment and the last value on study. Sponsor determined PCS values will be identified for specific laboratory parameters as outlined in Table 9 below.

Laboratory Parameter	Sex	Units	Criteria for PCS Values ( values)	Observed
			High	Low
Hematology		l		
Hemoglobin	Male	g/L	>185	<115
	Female	g/L	>170	<100
Hematocrit	Male	Fraction of 1	>0.55	< 0.385
	Female	Fraction of 1	>0.49	< 0.345
Platelet count		10^9/L	>600	<125
White blood cell		10^9/L	>15	<2.5

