Basophils		10^9/L	>0.5	NA
Eosinophils		10^9/L	>1.5	NA
Neutrophils		10^9/L	NA	<1.5
Lymphocytes		10^9/L	>6.0	<0.5
Monocytes		10^9/L	>1.4	NA
Chemistry		•		
Albumin		g/L	>70	<28
Blood urea nitrogen		mmol/L	>10.71	NA
Calcium		mmol/L	>2.75	<2.0
Chloride		mmol/L	>120	<90
Creatinine		mmol/L	>3xULN or >3x Baseline	
Gamma Glutamyl Transferase			>3xULN	
Glucose		mmol/L	>13.9	<2.8
Sodium		mmol/L	>150	<132
Potassium		mmol/L	>5.4	<3.3
Protein		g/L		<45
Bicarbonate		mmol/L	>34	<18
Phosphorus		mmol/L	>1.94	<0.61
Coagulation				
Prothrombin time		second	>=1.11 x ULN	NA

 Table 9. Potentially Clinically Significant (PCS) Values for Specific Laboratory

 Parameters

Laboratory Parameter	Sex	Units	Criteria for PCS Values ( values)	Observed
			High	Low
Partial thromboplastin time		second	>1.5 x ULN	NA

Liver function tests will be monitored closely for PCS values, and will be summarized for occurrence any time post-baseline for the following parameters for these PCS threshold (for condition involving more than one parameter, the results need to be from the same timepoint):

- Alanine Aminotransferase: >3xULN, >5xULN, >10xULN
- Aspartate Aminotransferase: >3xULN, >5xULN, >10xULN
- Alanine Aminotransferase or Aspartate Aminotransferase: >3xULN, >5xULN, >10xULN
- Alkaline Phosphatase: >1.5xULN, >2xULN
- Total Bilirubin: >1.5xULN, >2xULN
- Total Bilirubin >2xULN AND (Alanine Aminotransferase or Aspartate Aminotransferase >3xULN) [any time post-baseline, does not need to be measured at the same time point of assessment]
- [(Total Bilirubin >2xULN) AND Alkaline Phosphatase <2xULN (any time post-baseline, measured at the same time point of assessment)] AND [(ALT or AST >3xULN) AND Alkaline Phosphatase <2xULN, any time post-baseline, measured at the same time point of assessment]

By-participant listing of FSH and serology test results at screening will be provided.

By-participant listing of urine drug screen and alcohol breath test will also be provided.

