### 8.4.3. Electrocardiogram

A 12-Lead ECG will be performed after the participant has been resting in the supine position for at least 5 minutes. If there are both scheduled visit and unscheduled visit on the same date, all the assessments on that date are considered as the scheduled visit for the summary. A summary of raw values and change from baseline values will be summarized by each scheduled visit for the following ECG parameters: heart rate, PR, QRS, QT, and QTcF interval. This summary will also include the last values on treatment and on study. A by-participant listing of 12 lead ECG will also be provided for each of the ECG measurements.

ECG is evaluated by investigator as 'normal', 'abnormal, not clinically significant' and 'abnormal, clinically significant'. The number and percentage of participants with each category will be provided at baseline and each post-baseline scheduled assessment time point. If there are more than one evaluation at the same time point, the latest assessment from ECG vendor will be used for the summary.

Potentially clinically significant values of QTcF as outlined in Table 10 will be summarized by treatment for anytime on treatment, the last value on treatment and the last value on study.

12-Lead ECG	Units	Criteria for PCS ValuesC(Observed values)(		Criteria for PCSC values (Change from Baseline)		
		High	Low	Increase	Decrease	
QTcF	msec	>450 but ≤480>480 but ≤500	NA	≥30 to 60 >60	NA	
		>500				

 Table 10. Potentially Clinically Significant (PCS) Values for 12-Lead ECG Parameters

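### Outside ALT, AST, alkaline phosphatase and bilirubin, a participant whose only potentially clinically significant values follow the last dose is in no count unless the final value is one of them; and early-termination and unscheduled safety values have no analysis window at Days 14, 42 and 112

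*SAP*

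**What the plan says.** **Row definitions (SAP 8.4).**
- Anytime row: "Anytime on treatment is defined as measurement on or after first dose, on or before the date of last dose".
- Last on-treatment row: one value, with the same end date.
- Last on-study row: "Last value on study is defined as the last post-baseline value on or after the first dose of IP", up to the end of the study. This is again a single value.

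**Where these rows are used.** Section 8.4.2, on PCS laboratory results with limits in Table 9: "values for each laboratory parameter will be summarized by treatment for anytime on treatment, the last value on treatment and the last value on study". Section 8.4.3 says that QTcF values beyond the Table 10 limits "will be summarized by treatment for anytime on treatment, the last value on treatment and the last value on study". Section 8.4.4 gives the same three rows for the vital-sign criteria in Table 11.

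**The exception.** Section 8.4.2 gives ALT, AST, alkaline phosphatase and total bilirubin a separate rule: they "will be summarized for occurrence any time post-baseline". "Gamma Glutamyl Transferase" is in Table 9 and not in that list, so it follows the three-row rule.

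**Off-drug visits are planned.** Protocol 8.4.1: "Participants who discontinue IP will be invited by the investigator to complete all of the scheduled study visits and assessments". Protocol 7.4, on participants who cannot tolerate the lower dose: "Participants will be encouraged to continue to come in for the remaining study-related periodic assessments even after the IP discontinuation".

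**Visit mapping.** Under SAP 8.4, an early-termination (ET) or unscheduled safety value enters a by-visit row only if the scheduled value is missing and the value falls in that visit's window. The windows are taken from Table 4, the table for the WAIS-IV Coding Test. Its only post-baseline window is Day 64 to Day 98. Table 12 also schedules laboratory tests, ECG and vital signs at Days 14, 42 and 112.

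**The concern.** PCS tables exist to show, by arm, how many participants ever crossed a safety limit. Here the question asked depends on the parameter. For four liver analytes it is whether the limit was crossed at any time after baseline. For the rest it is whether the limit was crossed on drug, or at the very last measurement. A QTcF, potassium, GGT, platelet or blood-pressure value that crosses its limit after IP is stopped, and later returns inside it, can be missing from the count. The protocol expects participants who stop IP to keep attending, so such values can be foreseen.

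The mapping rule is a separate matter. It borrows windows built for a test done once after baseline and applies them to assessments done four times after baseline.

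**Working it through.** The plan states no figure on this point, so there is none to reproduce. The check applies the SAP's own definitions to the visit schedule.

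**Inputs.** Post-baseline safety visits at Days 14, 42, 84 and 112 (SAP Table 12); the three row definitions (SAP 8.4); the Table 4 window.

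**1. Condition for being missed.** The tables count participants, so an on-treatment PCS value for the same parameter already puts the participant in the anytime row. To be in no row, a participant needs all three of:
- a PCS value dated after the last dose;
- no PCS value for that parameter up to the last-dose date;
- a final on-study value that is not PCS.

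**2. Example participants** (values not mentioned are not PCS):

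| Last dose | PCS value | Final value | Three-row count | Any time post-baseline |
|---|---|---|---|---|
| Day 30 | Day 42 | Day 112, not PCS | none | yes |
| Day 50 | Day 84 | Day 112, not PCS | none | yes |
| Day 83 | Day 84 | Day 112, not PCS | none | yes |
| Day 84 | Day 112 | Day 119 unscheduled, not PCS | none | yes |
| Day 84 | Day 112 | Day 112, PCS | last on study | yes |
| Day 30 | ET, Day 37 | Day 37, PCS | last on study | yes |
| Day 30 | ET, Day 30 | Day 30, PCS | all three | yes |

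The third line shows that missing the dose on the day of the Day 84 visit is enough. The fourth shows that a repeat can displace a completer's Day 112 value. Table 12 allows out-of-range vital signs to be repeated once.

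**3. Exposure by schedule.** Nominal days, all visits attended, Day 112 value not PCS. Every post-stop visit except Day 112 is then outside all three rows.

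| Last dose | Post-stop visits | Outside every row |
|---|---|---|
| Before Day 14 | 14, 42, 84, 112 | 3 of 4 |
| Days 14–41 | 42, 84, 112 | 2 of 3 |
| Days 42–83 | 84, 112 | 1 of 2 |
| At the Day 84 visit | 112 | 0 of 1 |

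**4. Windows.** Days of each operational window in Table 12 that fall inside Table 4's Day 64–98:

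| Visit | Operational days | Inside Day 64–98 |
|---|---|---|
| Day 14 ±2 | 12–16 | 0 of 5 |
| Day 42 ±2 | 40–44 | 0 of 5 |
| Day 84 ±7 | 77–91 | 15 of 15 |
| Day 112 ±7 | 105–119 | 0 of 15 |

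Table 4 therefore serves 1 of the 4 post-baseline safety visits. Its limits agree with midpoints between adjacent safety visits: (42 + 84)/2 = 63, so the window opens on Day 64; (84 + 112)/2 = 98, where it closes. The midpoint before that is (14 + 42)/2 = 28.

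**The case against.** **The conditions are narrow.** The participant must have an off-drug PCS value, none on drug and a later final value that is not PCS. In practice this means stopping IP early and staying in the study, missing the dose at the Day 84 visit, or having an unscheduled or repeat value. This stands. A completer dosed at the Day 84 visit whose Day 112 value is final is not affected.

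**Other displays show these values.** This stands in part.
- By-participant data listings and PCS listings are planned.
- By-visit summaries by arm include the minimum and maximum (SAP 8.1), so an extreme value at a scheduled off-drug visit is visible.
- Shift tables cover hematology and biochemistry, but not coagulation, QTcF or vital signs.
- The investigator's ECG interpretation is tabulated by visit.
- Laboratory results judged clinically significant are captured as adverse events (SAP 8.4.2), and treatment-emergent events are counted by arm through the end of the study.

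None of these gives PCS incidence by arm for the values in question. What stays uncounted is mainly a transient crossing of a limit, off drug, that was not judged clinically significant.

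**The liver rule is a deliberate choice.** The SAP says that liver tests will be watched closely, and section 8.4 allows exceptions to its general rows. The protocol asks only that PCS values be summarised by treatment, which the SAP does. This stands: there is no contradiction within the SAP and no conflict with the protocol. It does not explain why the other parameters should lack the wider row.

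**The window rule can be executed.** Table 12 gives operational windows, and read literally the rule leaves ET and unscheduled values out of the Day 14, 42 and 112 rows. That is correct, and they can still enter the anytime and last-value rows. For ECG, an unscheduled assessment on the same date as a scheduled visit counts as that visit (SAP 8.4.3). But section 8.4 refers to no analysis window for these three visits, and nothing suggests that leaving the values out was intended.

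**Conclusion.** Both points hold and both are minor. The first follows from the row definitions alone. Its extent by schedule is as tabulated, assuming nominal visit days, full attendance and a Day 112 value that is not PCS. The documents give no rate for stopping IP and staying in the study, so the number of participants affected cannot be stated. The second concerns by-visit summaries only, and only when the scheduled value is missing.

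Three stronger readings are tempting and are not supported:
- *That ET values or all off-drug values drop out of the PCS tables.* They do not. An ET value that is the final value is counted in the last on-study row, and one taken on the last-dose date is also on treatment.
- *That the safety comparison is biased or a signal hidden.* The documents give no size or direction, the safety tables are descriptive without hypothesis testing, and the displays listed above remain.
- *That ET and unscheduled values have no place in the analysis at Days 14, 42 and 112 because the plan has no windows at all.* Operational windows exist; what is missing is an analysis window in the cross-reference.

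**What to change.** **PCS tables.** Add a row for any time post-baseline to the PCS summaries of Table 9 parameters, QTcF and vital signs, using the rule already applied to the four liver analytes. Keep the on-treatment and last-value rows. The cost is one row per table, from data already collected. The downside is small: the new row mixes some off-drug values with on-drug ones, which is why the strict rows should stay.

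**Windows.** In SAP 8.4, replace the reference to Table 4 with stated safety analysis windows for Days 14, 42, 84 and 112. Midpoints would give Days 2–28, 29–63, 64–98 and 99 onward, which keeps Table 4's Day 84 limits. The SAP does not say that Table 4 was built from midpoints, so this is one reasonable option. Narrower windows would serve if stated. The cost is one short table.

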## Sage Therapeutics, Inc. CONFIDENTIAL

Assessments	Screening Period	Baseline Period			Treati	nent Period			Follow-Up Period
	Days -35 to -8	Days -7 through -1	Day 1 a	Day 14 (±2 days)	Day 28 (±2 days) safety phone call b	Day 42 (±2 days) c	Day 63 (±2 days) safety phone call b	Day 84 (±7 days) d or ET	Day 112 (±7 days)
Urine drug test	х		Х	Х		х		Х	Х
Alcohol breath test	Х		Х	Х		Х		Х	Х
Pregnancy test o	X		Х					Х	
C-SSRS (Baseline/Screening Form)	X								
WAIS-IV Coding test r		Х						Х	

Assessments	Screening Period	Baseline Period			Treatr	nent Period			Follow-Up Period
	Days -35 to -8	Days -7 through -1	Day 1 a	Day 14 (±2 days)	Day 28 (±2 days) safety phone call b	Day 42 (±2 days) c	Day 63 (±2 days) safety phone call b	Day 84 (±7 days) d or ET	Day 112 (±7 days)
IP self-administration u					X (once dail	y in the mornir	.g)		
P dispensation v			Х	Х		Х			
IP accountability w						Х			
IP return x				Х		Х		Х	
Safety call assessment b					Х		Х		
AEs/SAEs y					Х				
Prior and concomitant medications z					Х				
bbreviations: AD = Alzheir	ner's Disease; A	E = adverse	event,						
		CDR = Cl	inical Dem	entia Rating;					
	COVID-19 = c								ET = ea
ermination; mmunodeficiency virus; IC	TF = informed c	onsent form:	IP = invest	igational produ		= follicle-stim	ulating hormone	; HIV = human MRI = magneti	
maging;	informed e	Jilsent Iorin,	II IIIvest	igational prod			· · · · · · · · · · · · · · · · · · ·	witci inagiieti	
event; WAIS-IV Coding Te								SAE = seri	ous adverse

a All tests at the Day 1 Visit will be conducted predose.

- b Phone check-in only for AEs/SAEs and changes to medical history or medications.
- c Within the SAGE-718 treatment arm, participants will receive 1.2 mg of SAGE-718 daily for the first 6 weeks (Day 1 Visit to Day 42 Visit [±2 days]), followed by 0.9 mg of SAGE-718 for the remainder of the Treatment Period (ie, beginning the first day after the Day 42 Visit). Dosing ends at the Day 84 Visit (±7 days). The placebo arm will receive matching placebo throughout the Treatment Period (12 weeks).
- d Dosing ends at the Day 84 Visit (±7 days). Participants who terminate early should perform all of the assessments that are scheduled for the Day 84 Visit (±7 days).

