### 8.4.4. Vital Signs

Vital signs will include height, weight, oral temperature(°C), respiratory rate (breaths per minute), heart rate (beats per minute [bpm]), and blood pressures (mmHg). Heart rate and blood pressure were collected in supine position and standing position at all scheduled time points.

Vital sign results and mean changes from baseline will be summarized by scheduled visit. It will also include the summary of last values on treatment and on study assessments. Potentially clinically significant values as outlined in Table 11 will be summarized by treatment for anytime on treatment, the last value on treatment and the last value on study. By-participant listing of vital signs will also be provided.

Vital Sign	Units	Criteria for PCS Values (Observed values)		Criteria for PCS values (Change from Baseline values)	
		High	Low	Increase	Decrease
Heart rate (supine and standing)	Beats/min	>120	<40	NA	NA
Respiratory Rate	Beats/min	>20	<8		
Systolic blood pressure (supine and standing)	mmHg	>180	<90	≥30	≥30
Diastolic blood pressure (supine and standing)	mmHg	>110	<50	≥20	≥20
Supine – Standing* Systolic Blood Pressure	mmHg	≥20			
Supine – Standing* Diastolic Blood Pressure	mmHg	≥10			
Orthostatic hypotension: supine – standing* SBP and DBP	mmHg	$SBP \ge 20$ and DBP $\ge 10$			

Table 11. Potentially Clinically Significant (PCS) Values for Vital Sign Parameters

Vital Sign	Units	Criteria for PCS Values (Observed values)		Criteria for PCS values (Change from Baseline values)	
		High	Low	Increase	Decrease
Possible orthostatic hypotension: supine – standing* SBP and DBP	mmHg	$SBP \ge 20$ or DBP $\ge 10$			

\* Supine – Standing means the difference of results between supine and standing positions.

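### Counts of potentially clinically significant (PCS) values based on observed limits include participants already over the limit at baseline; a treatment-emergent row would show new cases at little cost

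*SAP*

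**What the plan says.** SAP 8.4 defines the main window for the PCS summaries: "Anytime on treatment is defined as measurement on or after first dose, on or before the date of last dose". The definition after it reads "Last value on treatment is defined as the last post-baseline value between first dose of IP and up to the date of last dose of" (the investigational product), and the one for the last value on study is also limited to post-baseline values.

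The PCS counts then follow by domain:

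- **Laboratory (SAP 8.4.2, Table 9):** "The number and percentage of participants with potentially clinical significance (PCS) values for each laboratory parameter will be summarized by treatment". All three windows apply: anytime on treatment and the two last-value definitions.
- **Liver tests (SAP 8.4.2):** these "will be summarized for occurrence any time post-baseline for the following parameters".
- **QTcF (SAP 8.4.3, Table 10):** "Potentially clinically significant values of QTcF as outlined in Table 10 will be summarized by treatment for anytime on treatment" and for the two last-value definitions. There are observed bands and change-from-baseline bands.
- **Vital signs (SAP 8.4.4, Table 11):** "Potentially clinically significant values as outlined in Table 11 will be summarized by treatment for anytime on treatment" and for the two last-value definitions. Systolic and diastolic pressure have observed and change limits. Heart rate, respiratory rate and the four supine-minus-standing rows have observed limits only.

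None of these sections restricts the count to participants who did not meet the criterion at baseline, and none plans a row for newly arising PCS values. SAP Table 8 plans shift tables for clinical laboratory only. By SAP 8.4.2 these cover hematology and biochemistry and refer to the laboratory's normal ranges, not to the PCS limits.

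**The concern.** A reader will take a row of PCS values on treatment as a measure of what happened after dosing started. Where the limit applies to the observed value, the row mixes new cases with abnormalities that were present before dosing and persisted. In a randomized trial the pre-existing cases are expected in equal numbers in both arms, so they add the same amount to each row and shrink the ratio. No hypothesis testing of safety data is planned, so these rows will be compared by eye.

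Eligibility does not remove such participants. Exclusion criterion 10 rests on the investigator's view of clinical significance, without numeric limits, and covers the ECG and supine vital signs only. No criterion excludes an orthostatic drop, although orthostatic measurements are taken at Screening and on Day 1 in people aged 50 to 80. The SAP separates pre-treatment from treatment-emergent events for adverse events (8.4.1) but has no counterpart for PCS values.

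**Working it through.** **Which rows have a baseline reference**

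| PCS criterion | Baseline-relative criterion | Shift table |
|---|---|---|
| Heart rate, respiratory rate, four orthostatic rows | No | No |
| Systolic and diastolic pressure | Yes, separate change limits | No |
| QTcF | Yes, separate change bands | No |
| Creatinine | Yes, but joined by *or* to an absolute limit | Yes, on normal range |
| Other hematology, biochemistry and liver limits | No | Yes, on normal range |
| Coagulation | No | No |

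A change criterion cannot be met at baseline, so those rows are unaffected. The observed-value rows beside them are affected.

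**Size of the effect**

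The plan states no figure for this point. The only input from the documents is the arm size: 120 / (1 − 0.20) = 150 randomized, or 75 per arm, as stated. The rest are assumptions:

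- b: share of participants meeting the limit at baseline (5%, 15%, 25%), equal in both arms;
- s: share of those who still meet it on treatment (1, then 0.5), equal in both arms;
- p: rate of new cases among the others, 5% on placebo and 10% on SAGE-718, a true ratio of 2.0.

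Expected share in the planned row = b·s + (1 − b)·p. The difference between arms is (1 − b)(p₁ − p₀), because b·s cancels.

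With s = 1:

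| b | Placebo | SAGE-718 | Ratio | Difference |
|---|---|---|---|---|
| 0 | 5.00% | 10.00% | 2.00 | 5.00 points |
| 5% | 0.05 + 0.95 × 0.05 = 9.75% | 0.05 + 0.95 × 0.10 = 14.50% | 1.49 | 4.75 points |
| 15% | 0.15 + 0.85 × 0.05 = 19.25% | 0.15 + 0.85 × 0.10 = 23.50% | 1.22 | 4.25 points |
| 25% | 0.25 + 0.75 × 0.05 = 28.75% | 0.25 + 0.75 × 0.10 = 32.50% | 1.13 | 3.75 points |

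At b = 15% the planned rows are 75 × 0.1925 = 14.4 and 75 × 0.235 = 17.6 participants. Restricted to the 75 × 0.85 = 63.75 per arm not meeting the limit at baseline, they are 3.2 and 6.4. Dividing each difference by its standard error gives 0.64 for the planned rows and 1.08 for the restricted ones.

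If half of the baseline cases resolve (s = 0.5), at b = 15% the shares are 0.075 + 0.0425 = 11.75% and 0.075 + 0.085 = 16.00%. The ratio is 1.36 and the difference is still 4.25 points.

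Other inputs give the same pattern. With new onset of 4% and 12% (true ratio 3.0) and s = 1, the ratio reads 2.32 at b = 2% and 1.53 at b = 10%, where the difference falls from 8.0 to 7.2 points.

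**The case against.** The strongest case against is that PCS counts are not the main safety evidence. SAP 8.4 evaluates the secondary objective through the frequency and severity of treatment-emergent adverse events and withdrawals due to adverse events; the other safety endpoints are changes from baseline. Laboratory results that the investigator judges clinically significant become adverse events. Laboratory shifts use the worst on-treatment value, and participant listings allow any PCS case to be traced to its baseline. How many participants had a PCS value on treatment is a coherent descriptive question. All of this stands, and it makes the point an improvement, not an error.

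It also stands that the absolute difference shrinks only by the factor (1 − b), that full persistence is the worst case, and that neither standardized difference above would be notable. High prevalence is plausible mainly for the orthostatic rows. Nothing in the documents suggests it for limits such as platelets below 125 × 10⁹/L.

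A reader might further infer that Day 1 predose values will themselves be counted as on treatment. The definition of *anytime on treatment* lacks the post-baseline wording of the next two, and Protocol Table 2, footnote a, says "All tests at the Day 1 Visit will be conducted predose", that is, on the date of first dose. The documents do not support that inference as a planned result. SAP 8.1 uses clock time where it is collected and otherwise presumes a Day 1 assessment to precede dosing, and the window opens at the first dose, not at its date. The missing wording deserves a clarification only.

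What the objection does not answer is that no planned table shows, by arm, how many participants newly crossed an observed-value PCS limit.

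**Conclusion.** For PCS criteria on observed values (heart rate, respiratory rate, orthostatic drops, absolute blood-pressure and QTcF bands, and laboratory and liver limits), persistent pre-existing cases enter both arms' rows and pull the ratio toward 1. Under the 5% versus 10% illustration a doubling reads as 1.49 to 1.13 over baseline prevalence of 5% to 25%. This rests on assumed prevalence, onset and persistence; dilution is less if baseline cases resolve and nil if there are none. The gap is widest for vital signs, above all the rows without a change criterion.

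A reader might infer that pre-existing abnormalities will dominate these tables and hide any new signal. The documents do not support that. They give no baseline PCS rates, and a participant who met a limit at baseline but not on treatment is not counted in a post-baseline row. The adverse-event tables, change summaries, laboratory shifts and the QTcF and blood-pressure change criteria would also show new effects. The change is worth making as a low-cost improvement in what the tables can show.

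**What to change.** In SAP 8.4.2 to 8.4.4, for each observed-value PCS criterion:

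1. Add a treatment-emergent row. Its numerator and denominator are restricted to participants with a baseline value that does not meet that criterion. For the QTcF bands, the baseline should lie in neither that band nor a higher one; otherwise a fall from a higher band would count as new. A table of baseline against worst on-treatment PCS status would serve equally well.
2. Show the number of participants who met the criterion at baseline, by arm.
3. Keep the all-participant row, which answers its own question and retains participants who were already over the limit.

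As a clarification, add post-baseline to the definition of *anytime on treatment* in SAP 8.4, so that it agrees with the two definitions after it and with the Day 1 rule in SAP 8.1.

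The cost is SAP wording and table programming; the baseline values are already collected. The downside is one or two more rows per parameter and slightly smaller denominators, for example about 64 instead of 75 per arm at a baseline prevalence of 15%.
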